5.3 Exclusion of Specific Populations

Children and pregnant women are excluded from this first-in-human Phase 1 study because insufficient information is available on the safety of HydroVax-002 YFV to judge potential risks for children and pregnant women.

5.4 Inclusion of Vulnerable Participants

Not applicable.

5.5 Lifestyle Considerations

During this study, participants are asked to:

- Avoid getting pregnant during the study from the time of screening until 30 days after the second vaccination
- Use an acceptable contraception method, if a woman of childbearing potential, from 30 days before the first study vaccination until 30 days after the second study vaccination
- Use a medically acceptable form of contraception, if a sexually active male, until day 30 after the last vaccination
- Refrain from receiving another experimental agent or participating in another clinical trial with an interventional agent
- Refrain from donating blood during the study period
- Refrain from a major change in exercise routine or strenuous exercise from 72 hours before any dose of study vaccine/placebo and for 72 hours before each blood collection for clinical laboratory tests (Vaccination Days and Days 4 and 15 following each dose)
- Abstain from travel to areas known to be endemic with Yellow Fever virus until 6 months after vaccination

5.6 Screen Failures

Following consent, after the screening evaluations have been completed, the investigator or designee is to review the inclusion/exclusion criteria and determine the subject's eligibility for the study. If there is any uncertainty, the PI should make the decision on whether a potential subject is eligible for enrollment.

Only the following information will be collected on screen failures: demographics (age, screen number, sex, ethnicity, and race) and reason for ineligibility. Subjects who are found to be ineligible will be told the reason for ineligibility.

Individuals who do not meet the criteria for participation in this study (screen failure) because of a laboratory value that is outside the range of eligibility, but is thought to be due to an acute condition or due to laboratory error, may be repeated once

5.7 Strategies for Recruitment and Retention

5.7.1 Recruitment

Potential participants will be selected from existing participant registries, through advertising or by word of mouth in the Duke University, Durham, NC area and surrounding communities. Recruitment staff will contact interested individuals to assess their eligibility for this study. It is anticipated that the demographic composition of subjects for this study will be representative of the respective region.

The IRB will approve the recruitment process and all materials provided prior to any recruitment to prospective subjects directly.

Screening will begin with a brief discussion with study staff. Some people will be excluded based on demographic data and medical history (i.e., pregnant, prior travel, prior vaccination, etc.). Information about the study will be presented to potential subjects and questions will be asked to determine potential eligibility. Screening procedures can begin only after informed consent is obtained.

5.7.2 Retention

Retention of subjects in this trial is especially important for determining the primary and secondary endpoints. As such, after vaccination, participating subjects will be reminded of subsequent study visits and every effort will be made to accommodate the subject's schedule to facilitate follow-up within the specified visit window. Additionally, there are many circumstances that influence the ability to obtain outcome information after vaccination. Follow-up visits may be conducted by phone if in person visits are not feasible. Lastly, compensation strategies will be implemented to encourage subjects to return for follow-up assessments and sample collections.

5.7.3 Compensation Plan for Subjects

Compensation will be determined locally at the study site and in accordance with local IRB regulations and approval.

5.7.4 Costs

There is no cost to subjects for the research tests, procedures/evaluations, and study product while taking part in this trial. Procedures and treatment for clinical care may be billed to the subject, subject's insurance or third party.

6. STUDY PRODUCT

6.1 Study Product and Administration

In this dose escalation study, the first 13 subjects will be randomized (10:3) to receive two doses of either 1 mcg HydroVax-002 YFV IM injection or placebo IM injection 28 days apart. The second 12 subjects will be randomized (5:1) to receive two doses of 5 mcg HydroVax-002 YFV IM injection or placebo IM injection 28 days apart.

6.1.1 Study Product Description

6.1.1.1 Vaccine

The HydroVax-002 YFV vaccine is a yellow fever virus, Vero cell tissue culture-derived vaccine inactivated with hydrogen peroxide, formulated with 0.1% aluminum hydroxide. HydroVax-002 YFV drug product contains 5 mcg purified whole virus YFV formulated in a volume of 0.5 mL/dose with 0.1% aluminum hydroxide and 10% sorbitol, 0.001% polysorbate 80 in phosphate-buffer [pH = 7.5] with 350 mM sodium chloride. A single 0.5 mL dose of HydroVax-002 YFV may also contain residual amounts of Vero host cell DNA (<1 ng/0.5 mL) or Vero host cell protein (<300 ng/0.5). HydroVax-002 YFV does not contain antibiotics or preservatives. The stoppers used for single-dose vials do not contain latex.

6.1.1.2 Placebo and Diluent

Sodium Chloride Injection USP, 0.9% (NaCl 0.9%, Normal Saline) will be used as the placebo and diluent.

6.1.2 Dosing and Administration

Based on dosing group assignment, subjects will receive either 1 mcg, 5 mcg, or placebo per vaccination dose administered in the non-dominant arm as a 0.5 mL intramuscular (IM) injection on days 1 and 29. Following vaccination, subjects will be observed for a minimum of 30 minutes.

6.1.3 Dose Escalation

For this Phase 1 first-in-human trial, a conservative dose escalation design will be used, in which each dose group of 10 vaccine recipients, and a total of 5 placebo recipients, is split into two subgroups. The first subgroup, termed the sentinel subgroup, includes 3 vaccine and 1 placebo recipient. In each of the two (1 mcg and 5 mcg) dose phases, enrollment is halted after vaccination of the sentinel subgroup. This allows the opportunity to identify potential early vaccine related adverse events in this subgroup prior to exposure of additional subjects, a design which decreases the risk of multiple serious vaccine related adverse events compared to sequential vaccination of the entire dose group without halting [34]. After enrollment of the expanded subgroups, escalation to the next dose group will be delayed until 14 days of safety data following the second vaccination (corresponding to study Day 15) is available from all subjects in the preceding dose group.

6.1.4 Dose Modifications

Not applicable.

6.1.5 Overdosage

Overdosage is not anticipated in the context of a clinical trial. Subjects will be given intramuscular injections on Days 1 and 29. No study product will be administered outside the clinical setting.

6.2 6.2 Preparation/Handling/Storage/Accountability

6.2.1 Acquisition and Accountability

[REDACTED]

[REDACTED]

[REDACTED]

Sodium Chloride Injection USP 0.9% for placebo and diluent will be sourced by the Duke Investigational Drug Service.

After receipt of the study product, the principal investigator is responsible for distribution and disposition of these study products and has ultimate responsibility for drug accountability. The principal investigator may delegate to the research pharmacist responsibility for study vaccine accountability. The research pharmacist must maintain and document logs of receipt, accountability, vaccine dilution and dispensation, storage conditions, and disposal. These study product accountability and dispensing logs must be maintained in the study file.

Upon completion of the study and the final monitoring visit, used and unused vials of HydroVax-002 YFV and Placebo/diluent (sterile 0.9% NaCl) will be retained until monitored and released for disposition. For detailed information regarding final disposition of study vaccine and placebo/diluent see the protocol-specific MOP.

6.2.2 Formulation, Appearance, Packaging, and Labeling

HydroVax-002 YFV vaccine will be supplied to the investigative site in crystal zenith 2 mL vials containing 5 mcg of purified, inactivated whole YFV virus formulated with alum per 0.5 mL with stopper, crimp seals, and flip-off cap. Each vial will contain a fill volume of 0.6 mL. The study vaccine is a white, opaque, non-uniform suspension that becomes homogeneous upon shaking.

Sodium Chloride Injection USP 0.9% is a sterile, nonpyrogenic, isotonic solution of sodium chloride and WFI. It will be used to dilute the vaccine and will be used as the placebo.

Further details regarding formulation, packaging and labeling are included in the protocol-specific Manual of Procedures (MOP) and the Investigator's Brochure for the HydroVax-002 YFV vaccine.

6.2.3 Product Storage and Stability

Study vaccine and the normal saline placebo/diluent will be shipped and stored refrigerated at 2°C to 8°C. Study vaccine and the placebo/diluent should not be frozen.

During storage, HydroVax-002 YFV vials should be kept in a lightproof container. During storage, a clear liquid with a white precipitate will be observed; this is the alum adjuvant and this appearance is to be expected following refrigerated storage.

6.2.4 Preparation

Study vaccine preparation, including vaccine dilutions for the various dosing groups, will be performed by the site research pharmacist on the same day of study vaccine administration. Detailed information regarding the handling of vaccine, including preparation of the dilutions, labeling, storage, and administration of study vaccine will be provided in the protocol-specific MOP.

Aseptic technique will be used for the administration of each dose of study product using a sterile needle appropriate in length for each participant, as described in the protocol-specific MOP.

6.3 Measures to Minimize Bias: Randomization and Blinding

6.3.1 Treatment Assignment Procedures

Per International Conference on Harmonisation (ICH) guideline E6: Good Clinical Practice (GCP), screening records will be kept at the clinical site to document the reason why an individual was screened, but failed trial entry criteria. The reasons why individuals failed screening will be recorded in the Coordinating Center's (CC) Advantage eClinical® (Electronic Data Capture System).

Once consented and upon entry of demographic data and confirmation of eligibility for the trial, the subject will be assigned to a treatment arm within each dose group (low dose and high dose) subjects will be randomly assigned to receive the study test product or placebo. Subjects will be block randomized so that 1 of the first 4 sentinel subjects will receive placebo and the other 3 active vaccine. In the expanded groups, 7 of the 8 or 9 subjects will be randomized to vaccine and 1 or 2 to placebo. Subjects will receive the same treatment for both vaccinations.

6.3.2 Randomization

Enrollment of subjects will be done online using the enrollment module of Advantage eClinical®. The randomization code will be prepared by statisticians at the CC and included in the enrollment module for the trial. Advantage eClinical® will generate a treatment assignment for each subject after the demographic and eligibility data have been entered into the system. A designated individual at each site will be provided with a code list for emergency unblinding purposes, which will be kept in a secure place.

Instructions for use of the enrollment module are included in the Advantage eClinical® User's Guide. Manual back-up procedures and instructions are provided for use in the event that the site temporarily loses access to the Internet or the online enrollment system is unavailable.

6.3.3 Blinding and Masking Procedures

This is a partially-blinded clinical trial.

Study staff and investigators will not be blinded to dose group but, within dose groups, subjects, investigators, and study staff other than unblinded site research pharmacist (or other designated unblinded personnel administering study product) will be blinded as to the subject's treatment assignment (vaccine vs. placebo). Laboratory personnel performing antibody assays will be blinded to dose group and treatment assignment.

The randomization scheme will be generated by the CC and provided to unblinded study personnel (i.e., research pharmacists performing study vaccination preparations and unblinded study vaccine administrators) at the clinical site.

An unblinded site research pharmacist will prepare the study product and an unblinded research nurse will inject the study product per the randomization assignment. The pharmacist will conceal the contents of the syringe by wrapping the syringe barrel with an overlay, opaque tape, or other equivalent material. In addition, the subject will be asked to look away when the vaccine is being administered.

The unblinded site research pharmacist and unblinded research nurse will not be involved in study-related assessments or have subject contact for data collection following study vaccine administration.

6.3.3.1 Unblinding

A copy of subject treatment assignments will be retained at the site in a secure file by the unblinded staff. In the event of a medical emergency when knowledge of the treatment assignment will influence subject's care, the Principal Investigator may be provided with the treatment assignment. The Principal Investigator must contact NTI and document the event with information regarding the reasons for unblinding. After discussion with NTI, the Principal Investigator may receive the treatment assignment from the data coordinating center or if necessary, from the on-site secure file by the unblinded staff.

6.4 Study Intervention Compliance

Each dose of study product will be administered by a member of the clinical research team who is qualified and licensed to administer study product. Administration site, date, and time will be documented on the case report form (CRF) and entered into the eCRF.

6.5 Concomitant Therapy

All concomitant medications taken within 60 days prior to signing the ICF will be reviewed with subjects to determine stability of chronic diseases and eligibility. Medications reported in the eCRF are limited to those taken

within 30 days prior to the first dose of study vaccine. Concomitant medications will be reviewed at every study visit through Visit 07 (29 days following receipt of the second dose of study product).

Women of childbearing potential in a heterosexual relationship must agree to use true abstinence or use at least one acceptable primary form of contraception through 30 days following the second dose of study vaccine.

Prohibited medications:

- Medications that may be associated with impaired immune responsiveness including immunosuppressive or immunomodulating therapies.
- Anticancer chemotherapy within 3 years prior to vaccination.
- Medications used to control seizures within the past 3 years.
- Daily bronchodilators, oral or parental steroids, theophylline, or inhaled corticosteroids to treat an asthma exacerbation within the past year.
- Oral, parenteral, intra-articular, chronic topical steroids or high-dose inhaled steroids within 30 days.
- Investigational drug, vaccine, biologic, blood product, or medication within 30 days prior to receipt of the first dose of study product or during the study period.
- A live vaccine within 30 days of receipt of study product.
- An inactivated vaccine or allergy desensitization shot within 14 days of receipt of study product.
- Blood products or immunoglobulin during the six months prior to enrollment.

6.5.1 Rescue Medicine

Not applicable.

7. Study Intervention Discontinuation and Participant Discontinuation/Withdrawal

7.1 Halting Criteria and Discontinuation of Study Intervention

7.1.1 Study Halting Criteria

Additional enrollment and study interventions/administration of study products in this trial will be halted for SMC review/recommendation if any of the following are reported:

- Any subject experiences ulceration, abscess, or necrosis at the injection site related to study product administration.
- Any subject presents with laryngospasm, bronchospasm, hypotension or anaphylaxis occurring within 24 hours following product administration that is considered related to study product.
- Two or more subjects experience generalized urticaria (defined as occurring at more than two body parts) within 72 hours after administration of study product that is considered related to study product.
- Any subject experiences an SAE after administration of study product and prior to the subject's last visit that is considered related to study product.
- Two or more subjects who received at least one dose of study vaccine to date, cumulative to all study vaccine administrations, across all treatment arms, experience the same Grade 3 (unsolicited AE or safety laboratory), in the same HLT by MedDRA coding, considered related to study product.

This trial will also be halted for SMC review/recommendation if, within 7 days after administration of either study vaccination, any of the following occurs:

- Three or more subjects who received at least one dose of study vaccine to date, cumulative to all study vaccine administrations, across all treatment arms, experience the same severe (Grade 3) study vaccine-related injection site reaction. Erythema and induration (hardness)/edema (swelling) will also be measured in mm but size will not be used as halting criteria.
- Three or more subjects who received at least one dose of study vaccine to date, cumulative to all study vaccine administrations, across all treatment arms, experience the same severe (Grade 3) study vaccine-related subjective systemic reaction, for which the severity (grade) is corroborated by study personnel.
- Three or more subjects who received at least one dose of study vaccine to date, cumulative to all study vaccine administrations, across all treatment arms, experience the same severe (Grade 3) study vaccine-related quantitative systemic reaction.

Grading scales for solicited injection site and systemic (subjective and quantitative) reactions are included in Section [8.5.1.1](#).

Grading scales for clinical safety laboratory AEs are included [Appendix A](#).

If any of the halting rules are met following any subject receipt of any study vaccination, then this trial will not continue with the remaining enrollments or study vaccinations without a review by and recommendation from the SMC to proceed.

NTI retains the authority to suspend additional enrollment and study interventions/administration of study products during this trial, as applicable.

NTI is empowered to stop enrollment and study vaccinations if AEs that meet the halting criteria are reported.

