7.2 Participant Withdrawal from the Study and Replacement

7.2.1 Participant Withdrawal

Subjects may voluntarily withdraw their consent for trial participation at any time and for any reason, without penalty or loss of benefits to which they are otherwise entitled.

The site PI or appropriate sub-investigator may also withdraw a subject from receiving the study vaccine for any reason.

A subject may withdraw or be withdrawn from the study for the following reasons:

- Medical disease or condition, or any new clinical finding for which continued participation, in the opinion of the site PI or appropriate sub-investigator, would compromise the safety of the subject, or would interfere with the subject's successful completion of this trial, or would interfere with the evaluation of responses (for example, has baseline significant laboratory abnormalities).
- The subject withdraws consent.
- Subject no longer meets eligibility criteria (see Sections [5.1](#) and [5.2](#)). Note: Medication changes in the 60 days prior to enrollment, as specified in Subject Inclusion Criterion (See Section [5.1](#), Point Number [5](#)), are exclusionary for receipt of the first study vaccination only.
- As deemed necessary by the site PI or appropriate sub-investigator for noncompliance or other reasons.
- The subject is lost to follow-up.
- The study is terminated.
- Any reason that, in the opinion of the investigator, precludes the subject's participation in the study.
- New information becomes available that makes further participation unsafe.

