8.5.3 Classification of an Adverse Events

The determination of seriousness, severity, and causality will be made by an on-site investigator who is qualified (licensed) to diagnose, provide a medical evaluation of adverse events, and classify adverse events based upon medical judgment. This includes but is not limited to physicians, physician assistants, and nurse practitioners.

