10.1.6 Safety Oversight

10.1.6.1 Safety Monitoring Committee (SMC)

The study oversight will be conducted by a SMC which is an independent group of experts that will be established by NTI to monitor subject safety and advise NTI. SMC members will be separate and independent of study personnel participating in this study and should not have scientific, financial or other conflicts of interest related to the study. The SMC will consist of members with appropriate expertise to contribute to the interpretation of the data from this trial.

The primary responsibilities of the SMC are to:

- Review and evaluate the accumulated study safety data in a blinded fashion for participant safety after the low dose cohort prior to proceeding to the high dose cohort, study conduct and progress, and
- Make recommendations to the sponsors concerning the continuation, modification, or termination of the trial.

The operating rules of the SMC will be established in conjunction with NTI guidelines.

The SMC will review the safety laboratory results, reactogenicity data, and adverse event information collected through day 15 following Dose 2 for the Low Dose Cohort. SMC approval is required prior to initiation of enrollment in the High Dose Cohort.

The SMC may also be asked to review safety information on the low dose or high dose sentinel groups as documented in Section [10.1.6.2](#).

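### Protocol 7.1.1 halts dosing automatically, but 10.1.6.1 makes the suspend instruction wait for SMC-chair approval and reserves any suspension to the sponsor

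*Protocol*

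**What the plan says.** Protocol 7.1.1 is mandatory and names no approver: "Additional enrollment and study interventions/administration of study products in this trial will be halted for SMC review/recommendation if any of the following are reported". Once any rule is met, "this trial will not continue with the remaining enrollments or study vaccinations without a review by and recommendation from the SMC to proceed". The same section adds that the sponsor "retains the authority to suspend additional enrollment and study interventions/administration of study products during this trial" and may stop enrollment and vaccination when qualifying events are reported.

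Protocol 10.1.6.1 sets out the steps that follow a trigger:

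- The blinded medical monitor reviews the event within 24 hours of the report.
- After confirmation, the coordinating center alerts the SMC chair with a written narrative and tells the site PI that a rule was triggered.
- The coordinating center instructs the site to suspend enrollment and dosing once the chair approves.
- Concurrently with the site notification, the sponsor is told that activities are already paused.
- The site waits for the sponsor's directions before resuming.
- The paragraph closes by giving the sponsor sole authority over any suspension, temporary or permanent.

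The committee's procedures lie outside the protocol: "The operating rules of the SMC will be established in conjunction with" the sponsor's guidelines. They were not available for this review.

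**The concern.** These are the participant-protection rules of a first-in-human trial. They mainly protect people who have not yet been dosed when someone else has had a serious reaction. A stopping rule should have one meaning and should fail safe.

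Here one section makes the halt follow from the report itself. The other makes the operative instruction depend on a named person's approval and gives the suspension decision to a third party. A site that works from 10.1.6.1, the only text describing how it is told to stop, could reasonably wait for the instruction. While it waited, it could give further doses after a related SAE or anaphylaxis.

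**Working it through.** **Comparing the text.** No figure in the plan bears on this point, so the check is a comparison of the two sections by what the chair does.

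| SMC chair | Under 7.1.1 | Under 10.1.6.1 |
|---|---|---|
| Approves | Halted since the report | Site instructed to suspend |
| Silent | Halted until the SMC recommends proceeding | No instruction; no deadline, deputy or default stated |
| Declines | Halted until the SMC recommends proceeding | No instruction; no next step stated |

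The 24 hours applies to the monitor's review only. No sentence says which section prevails. Section 10.1.6.1 also disagrees with itself: the chair's approval releases the instruction, the sponsor hears of a pause already in force, and yet only the sponsor may decide on a pause.

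**Which rules the site can recognise first.** Section 7.1.1 lists eight rules. Three need one subject: injection-site ulceration, abscess or necrosis; a related SAE; and the acute-reaction rule, "Any subject presents with laryngospasm, bronchospasm, hypotension or anaphylaxis occurring within 24 hours following product administration" and judged related. For these the site holds the relevant judgment, since "The determination of seriousness, severity, and causality will be made by an on-site investigator". The other five need counts across subjects (two need at least 2 subjects, three need at least 3). One of those depends on events falling "in the same HLT by MedDRA coding, considered related to study product". A confirmation step is reasonable for these five.

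**Illustrative exposure.** Assumptions: subjects enter at an even pace, safety reviews take no time, and the Group 1 hold runs to Day 15 after dose 2 (Protocol 1.1.3).

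- Doses: 25 × 2 = 50. Enrollment of 3.5 to 4 months (Protocol 1.1.2) is 106.5 to 121.8 days. The last second dose falls 28 days later, so dosing spans 134.5 to 149.8 days.
- Average: 50/149.8 = 0.334 and 50/134.5 = 0.372 doses per day. Multiplied by 7, this is 2.3 to 2.6 per week.
- Holds without first doses: 7 + (28 + 14) + 7 = 56 days, leaving 50.5 to 65.8 open days. The first-dose rate r is 25/65.8 = 0.380 to 25/50.5 = 0.495 per day.
- Dosing is densest when expanded-cohort first doses overlap with sentinel second doses, at 2r per day. In Group 1 the overlap lasts 13/r − 21 days. If that is at least 7, the busiest week holds 14r doses; if it is shorter, the week holds 13 − 14r. These meet at r = 13/28 = 0.464, giving 14 × 0.464 = 6.5 doses (enrollment of 56 + 25/0.464 = 109.8 days, about 3.6 months).
- In Group 2, with 12 subjects, the two expressions are 14r and 12 − 14r. They meet at r = 12/28 = 0.429, giving 6.0 doses (56 + 25/0.429 = 114.3 days, about 3.75 months).
- If only the monitor's full 24 hours elapse, exposure averages 0.33 to 0.37 dose and is at most 2 × 0.495 = 0.99.

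Protocol 1.1.8 ends the Group 1 hold at Day 8 instead. Then r is 25/72.8 = 0.344 to 25/57.5 = 0.435, and the peaks are 14 × 0.435 = 6.1 in Group 1 and 6.0 in Group 2. A trigger during a sentinel hold finds enrollment already stopped and sentinel second doses already withheld.

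**The case against.** The strongest reply is that the sections can be read together. Section 7.1.1 states the rule, and 10.1.6.1 describes who tells whom; the amendment history describes that change as one to the notification process. Telling the sponsor that activities are paused fits a halt already in force. The sentence on the sponsor's sole authority follows the SMC's recommendations on continuation, and the SMC's role is advisory, so it may mean only that the committee advises and the sponsor decides.

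Much of this stands. A missing instruction is not permission to dose. Section 7.1.1 already makes stopped the default, and a chair's silence is not an SMC recommendation to proceed. A site that stops at once complies with the protocol. The notice to the site PI is not clearly conditional on the chair. The sponsor can suspend alone, and the site PI "may also withdraw a subject from receiving the study vaccine for any reason". The SMC's operating rules might set a response time or name a deputy.

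It does not dissolve the conflict. An automatic halt cannot stand beside a suspension decision that belongs only to the sponsor and an instruction that needs approval. The sponsor's and PI's powers are discretionary and are not written as a fallback for the chair step. The individual halting criteria in 7.1.2 mainly protect the subject who had the event. A deadline in the operating rules would not settle what happens if the chair declines.

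One further objection limits the remedy. Hypotension has no grading threshold in Table 15, and 8.5.3.2 lets relatedness rest on timing alone. A pause on the bare appearance of any single-subject trigger would therefore be debatable; it should follow the investigator's judgment that the rule is met.

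**Conclusion.** The point holds as a should-fix wording conflict in a safety rule, and the text is wrong as written. The two sections differ on who stops dosing and when, and neither is given precedence.

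A reader might infer that 10.1.6.1 lets dosing go on until the chair answers, or that the protocol has no default if the chair is silent. The documents support neither: 10.1.6.1 contains no permission to dose, and 7.1.1 supplies the default. What is missing is a fallback for the instruction, not for the halt itself.

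A reader might also take the dose figures as a forecast. They are rates: about 2.3 to 2.6 doses per week of delay on average, and up to about 6.5 in Group 1 or 6.0 in Group 2 in the busiest week. They rest on even pacing and reviews that take no time. How long a chair would take is unknown, and the only interval the protocol states is 24 hours. The conclusion rests on the text and does not depend on these figures.

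**What to change.** Amend Protocol 10.1.6.1 as follows.

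- (a) State that the 7.1.1 halt takes effect without chair or sponsor approval: on report where the investigator judges that a single-subject rule is met, and otherwise no later than the medical monitor's confirmation within 24 hours.
- (b) Remove the chair's approval as a condition for instructing the site to suspend. The chair would still be alerted and the SMC would still review.
- (c) Limit the sentence on the sponsor's exclusive decision to resumption after an SMC recommendation, further discretionary suspension, or termination.

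This is a wording amendment. Its cost is an occasional short pause for an event later found not to meet a rule.
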